12.1.1.3 Adverse events of interest

An AE of interest is any AE which is listed in the European Risk Management Plan, or meets another commitment requiring nonstandard expedited reporting, even if the AE does not fulfill the expedited reporting criteria of "serious," "unexpected," and "associated with the use of the drug." The following AEs of interest will be reported as SAEs, even if not meeting the definition as outlined in Section 12.1.1.2:

- Serious infections including opportunistic infections
- Malignancies including lymphoma
- Congestive heart failure
- Demyelinating-like disorders
- Aplastic anemia, pancytopenia, thrombocytopenia, neutropenia and leucopenia
- Serious bleeding events
- Lupus and lupus-like illness
- Serious skin reactions (eg, Stevens Johnson Syndrome, toxic epidermal necrosis, and erythema multiforme)
- Potential Hy's Law, defined as $\geq 3 \times \text{ULN}$ ALT or AST with coexisting $\geq 2 \times \text{ULN}$ total bilirubin in the absence of $\geq 2 \times \text{ULN}$ ALP, with no alternative explanation for the biochemical abnormality, must ALWAYS be reported to UCB as an AE of special interest (ie, without waiting for any additional etiologic investigations to have been concluded). Follow-up

information should then be reported if an alternative etiology is identified during investigation and monitoring of the subject.

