The table below summarizes the approach to investigate PDILI.

Table 12–2: Required investigations and follow up for PDILI

Laboratory value			Immediate		Follow up	
ALT or AST	Total bilirubin	Symptoms ^a of hepatitis or hypersensitivity	Consultation requirements	Actions	Testing	Evaluation
≥3xULN	≥2xULN ^b	NA	Hepatology consult. ^c	Immediate, permanent IMP discontinuation.	Essential: Must have repeat liver chemistry values and additional testing completed ASAP (see Section 12.2.1.3); recommended to occur at the site with HCP.	Monitoring of liver chemistry values at least twice per week until values normalize, stabilize, or return to within baseline values. ^d
≥8xULN	NA	NA	Medical Monitor must be notified within 24 hours (eg, by laboratory alert) and subject discussed with Medical Monitor ASAP.			
≥3xULN	NA	Yes		Immediate, temporary or permanent, IMP discontinuation.		
≥3xULN (and ≥2x baseline) and <5xULN	<2xULN	No	Discussion with Medical Monitor required if the criterion that allows for IMP continuation is met.	Further investigation > immediate IMP discontinuation not required (see Section 12.2.1.2).	Not required unless otherwise medically indicated (at discretion of Investigator).	

Table 12–2: Required investigations and follow up for PDILI

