10.2 Adverse events

Definitions and Data Handling Conventions

AEs recorded on the Baseline day will be regarded as ‘treatment emergent’. AEs occurring either before study drug administration (pre-treatment) or more than 70 days after last study drug administration will not be considered to be treatment emergent (TEAE). If a subject dies during the treatment period (timeframe: first study drug administration to last study drug administration +70 days), then the period for TEAEs will end with the death date. If a subject

has a Safety follow-up visit that extends beyond 70 days after the last study drug administration, then the period for TEAEs for that subject will end at the last study drug administration + 70 days.

Non treatment emergent AEs will only be listed separately.

Only AEs occurred at or prior to the visit of Week 24 will be included in the interim analysis.

Adverse events that occur on the Week 16 visit date will be attributed to the initial randomized treatment. The only exception to this definition is for the following types of events:

- Those which code to a HLT of “Injection Site Reactions”
- Those which have been designated as an Injection Reaction on the AE CRF and do not code to an SOC of “Investigations”
- Those which have been identified as a hypersensitivity reaction or an anaphylactic reaction

When any of these events occur on the Week 16 visit date, the AE will be attributed to the treatment received at Week 16.

In general, AEs will be allocated to the treatment group based on the dose most recently received.

The following rules will be applied to impute partial onset dates for AEs:

If the AE onset date is completely unknown, then use the date of first dose in the Initial Period.

If only the year is specified:

If the year of first dose in the Initial Period is the same as the year of onset, then use the date of first dose in the Initial Period.

If the year of first dose in the Initial Period is not the same as the year of onset, then use January 1 of the year of onset.

If only the month and year are specified:

If the month and year of first dose in the Initial Period is the same as the month and year of onset, then use the date of first dose in the Initial Period.

If the month and year of onset is after the month and year of first dose in the Initial Period and prior to the month and year of first dose in the Maintenance Period, then use the 1st of the month.

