In order to meet the above criteria, a subject must experience the elevation in bilirubin and ALT or AST at the same visit. For example, a subject who experiences a ≥2 x ULN elevation of bilirubin at one visit and a 3 x ULN elevation in ALT (or AST) at a subsequent visit has not fulfilled the Hy’s law criteria.

Other liver function test elevations that are of interest for summary purposes are:

- 3x, 5x, 8x ULN elevations of AST,
- 3x, 5x, 8x ULN elevations of ALT,
- 3x, 5x, 8x ULN elevations of either AST or ALT,
- 1x, 1.5x ULN elevations of Bilirubin
- 3x ALP

For determining cases of Hy's Law and other liver function test elevations, only post-Baseline assessments are considered. Pre-treatment and Safety Follow-up assessments are excluded. Additionally, assessments collected more than 70 days after the last dose of study treatment are excluded.

Lab Data Summary by Period

Initial Period

All summaries for the Initial Period will be presented by treatment group for the SS and the CSS.

Hematology and chemistry absolute and change from Baseline values will be summarized by visit using descriptive statistics for continuous data. In addition, the summaries will include descriptive statistics within the Initial Period for the end of treatment, minimum post-Baseline, and maximum post-Baseline values.

Shift from Baseline tables for lab values based on the normal range will be presented within the Initial Period for the end of treatment, minimum post-Baseline and maximum post-Baseline values. The shift categories will be low, normal, high, and missing.

The number and percent of subjects with markedly abnormal (\geq grade 3 by CTCAE) hematology or chemistry values will be summarized by visit and for any visit during the Initial Period. For the "any visit" summary, only values while on study treatment will be considered, meaning that the Baseline measurement will not be considered.

Shift from Baseline tables for lab values based on the markedly abnormal lab values will be presented within the Initial Period for the end of treatment, minimum post-Baseline, and maximum post-Baseline. The shift categories will be markedly abnormal, not markedly abnormal, and missing.

The number and percent of subjects meeting Hy's law criteria and other liver function test elevations specified above at any visit while on study treatment (i.e., Baseline excluded) during the Initial Period will be summarized.

Combined Initial and Maintenance Period

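### The Hy's Law and liver-elevation tables leave out Safety Follow-up tests and tests after Week 52, although adverse events are counted to 70 days after the last dose

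*SAP*

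**What the plan says.** SAP 10.3 sets the rule in three consecutive sentences. The first reads: "For determining cases of Hy's Law and other liver function test elevations, only post-Baseline assessments are considered". The second reads: "Pre-treatment and Safety Follow-up assessments are excluded". The third reads: "Additionally, assessments collected more than 70 days after the last dose of study treatment are excluded".

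The table descriptions add two limits. The Initial Period table counts subjects who meet the criteria "at any visit while on study treatment (i.e., Baseline excluded") during that period. The second table uses the same wording, with blinded or open-label treatment named, for the Combined Initial and Maintenance Period. SAP 3.2.3 defines the combined period as Baseline to Week 52, and Table 3-1 assigns data from the day after the Week 52 visit to the SFU Period. SAP 10.3 admits unscheduled and repeat tests to over-time tables only if they were collected in the period being summarized.

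For adverse events, SAP 10.2 says that those occurring "more than 70 days after last study drug administration will not be considered to be treatment emergent". Events up to day 70 are therefore included in the final analysis.

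Protocol 8.29 draws biochemistry at Safety Follow-up, which Protocol 8 places 10 weeks after the last dose, -3/+14 days. After certain liver results stop treatment, Protocol Table 12-2 requires the following: "Monitoring of liver chemistry values at least twice per week until values normalize, stabilize, or return to within baseline values". Protocol 12.1.1.3 says that potential Hy's Law "must ALWAYS be reported to UCB as an AE of special interest".

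**The concern.** Two windows apply to the same event. An adverse event that starts on day 40 after the last dose is treatment-emergent. A liver test on day 40 that meets the Hy's Law criteria may not reach the table meant to count such tests. The 70-day sentence suggests that off-drug tests were meant to count, but the Safety Follow-up exclusion and the period limit take most of them out again.

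The liver table is the only place where the SAP applies the combined ALT/AST, bilirubin and ALP criteria. The markedly abnormal tables treat ALT, AST and bilirubin separately. The hepatic-events summary in SAP 10.2 uses five SMQs on coded terms. The SAP's list of adverse events of interest has no entry for potential Hy's Law, although the protocol's list does. In a table where a single case changes the message, a reader would take a zero to mean that no such case occurred within the safety window.

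**Working it through.** No power or alpha figure bears on this. The check is day arithmetic and a reading of the rules together.

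**1. Completers: where Week 52 falls.** The last planned dose is Week 50 (SAP 7).
- Week 52 falls (52 − 50) × 7 = 14 days after the last dose.
- The adverse-event window runs to day 70, so 70 − 14 = 56 days, or 56/70 = 80%, lie after Week 52.
- No visit is scheduled in those 56 days before Safety Follow-up. Unscheduled liver monitoring can take place there.

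**2. Safety Follow-up against the 70-day limit.**
- Permitted window: 70 − 3 = day 67 to 70 + 14 = day 84, which is 84 − 67 + 1 = 18 days.
- Days that also satisfy the 70-day limit: 67 to 70, so 4 of 18 (22%). This is a share of days, not of subjects.
- Deleting the Safety Follow-up exclusion alone would therefore leave tests on days 71 to 84 excluded by the third sentence.

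**3. Illustration in a completer (invented values).** At Week 52: ALT 9xULN, bilirubin 1.5xULN. Five days later: ALT 7xULN, bilirubin 2.3xULN, ALP below 2xULN. SAP 10.3 requires both elevations at one visit, so only the second test qualifies for Hy's Law. It falls on day 14 + 5 = 19.

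| Condition | Met on day 19? |
|---|---|
| Post-Baseline | Yes |
| Not the Safety Follow-up visit | Yes |
| Within 70 days of last dose | Yes |
| Within Combined Initial and Maintenance Period | No |

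The case is lost through the period limit alone, without relying on the on-treatment wording. An adverse event starting that day would be treatment-emergent.

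**4. Early stoppers.** Table 3-1 footnote b starts the SFU Period the day after the last visit before the safety visit. If a monitoring attendance counts as a visit, monitoring stays in the treatment period. If the last visit means the Withdrawal Visit, later monitoring moves into the SFU Period. The order is not fixed: Protocol 6.3 calls for the Early Withdrawal Visit once treatment has been withdrawn, while 6.3.1 says that subjects with potential liver injury should not be withdrawn until monitoring is complete. The SAP does not say which tests count.

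**5. Who is affected among subjects stopped on a liver rule.** A subject stopped for ALT/AST ≥3xULN with bilirubin ≥2xULN, and with ALP below 2xULN, already qualifies on the triggering test, because the SAP needs no confirmation. Those exposed were stopped without the bilirubin limit being met, chiefly for ALT/AST ≥8xULN or ≥3xULN with symptoms, and reach bilirubin 2xULN later. Table 12-2 also stops subjects whose values stay at or above 5xULN after two weeks; the same reasoning applies to them.

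**6. Scale.** One case in a randomized CZP arm is 1/50 = 2%. Denominators in the combined-period table differ, because subjects move between dose groups.

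**The case against.** The best defence is that the sentences work as cumulative filters: post-Baseline, not Safety Follow-up, not beyond day 70. The 70-day sentence has a purpose only if off-drug tests can count, and the on-treatment phrase is explained in its own parenthesis as leaving out Baseline. Tests taken after a stop, but before withdrawal and Week 52, are then eligible. This is the better reading, and it stands. Even a literal on-treatment reading might keep tests in the first 14 days, since SAP 10.1 counts exposure to last dose + 14 days.

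A reader might infer that liver cases arising after the protocol stops treatment are, in general, not counted. The documents do not support that, for the reason just given and because many such subjects qualify on the test that stopped them. A reader might also blame the SAP rule for the 80% gap in step 1. That gap comes mainly from the visit schedule: the rule removes one scheduled test and any unscheduled ones.

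It is also fair to say that the signal is not lost. Protocol 12.2.1 requires every potential liver-injury event to be reported as an adverse event, and unscheduled results are listed. Excluding Safety Follow-up from a laboratory table is an open choice, and a legitimate one. None of this gives the reader a count by the Hy's Law criteria over the safety window, and for completers the 70-day sentence admits nothing after Week 52.

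**Conclusion.** The point holds in a limited form. Two exclusions follow from the text: elevations first seen at Safety Follow-up, and those first seen in unscheduled monitoring after Week 52 in completers. The second assumes that the Week 52 end of the combined period applies to laboratory tables as SAP 3.2.3 defines it; SAP 10.2 extends the window explicitly for adverse events, and 10.3 does not. For early stoppers the matter is an ambiguity, not an exclusion.

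The documents give no basis for estimating how many cases would be missed; zero is quite possible with about 125 plaque subjects. The 2% in step 6 shows what one case is worth and is not an expected loss. The defect is one of counting and reporting. It does not touch the efficacy conclusions, and no view is taken on the liver stopping rules themselves.

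**What to change.** Replace the three sentences in SAP 10.3 with one window, for the Hy's Law and liver-elevation tables only:

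- Count every liver test after the first dose (scheduled, unscheduled including liver-injury monitoring, Withdrawal and Safety Follow-up) up to last dose + 70 days, regardless of the Week 52 boundary.
- Delete the Safety Follow-up exclusion, and replace the on-treatment phrase in both table descriptions with post-Baseline.
- In the Initial Period table, keep the Week 16 cut for subjects who continue into Maintenance, as SAP 10.2 does for adverse events.
- List separately any Safety Follow-up result after day 70 that meets the criteria; the visit window allows days 71 to 84.
- Mark each counted case as on-drug or post-dose.

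The last item deals with the main drawback: some off-drug elevations will be attributed to the last treatment received. The cost is SAP wording and programming. The results are already collected, and no visit or sample is added.

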10.4 Vital signs, physical findings, and others related to safety

10.4.1 Vital signs

Definitions and Data Handling Conventions

All summaries will be based on observed case values. For tables where data are summarized by visit, unscheduled and repeat visits will not be summarized, but these data will be included in listings.

In the case that vital signs are collected one or more days following the scheduled visit date, in which the drug was administered, these vital signs results will not be summarized as part of that visit (for by-visit presentations). However, these vital signs results will be considered for tables where multiple measurements over a period of time are considered (as in shift tables) so long as they are in the appropriate period being summarized.

Definitions for the normal range for blood pressure values are given in the table below.

Table 10–4: Definitions of normal range for blood pressure values

Parameter (unit)	Low	High
Systolic blood pressure (mmHg)	<90	>140
Diastolic blood pressure (mmHg)	<60	>90

Definitions of markedly abnormal values for systolic and diastolic blood pressure are given in the table below.

Table 10–5: Definitions of markedly abnormal blood pressure values

Parameter (unit)	Markedly Abnormal Low	Markedly Abnormal High
Systolic blood pressure (mmHg)	<90 and a decrease from Baseline of ≥ 20	>180 and an increase from Baseline of ≥ 20
Diastolic blood pressure (mmHg)	<50 and a decrease from Baseline of ≥ 15	>105 and an increase from Baseline of ≥ 15

Data Summary by Period

Initial Period

All summaries for the Initial Period will be presented by treatment group for the SS and CSS.

Absolute and change from Baseline blood pressure values will be summarized by visit using descriptive statistics for continuous data. Weight will be summarized in a similar manner.

Shift from Baseline tables for blood pressure values based on the normal range will be presented within the Initial Period for the end of treatment, minimum post-Baseline and maximum post-Baseline values. The shift categories will be low, normal, high, and missing.

Shift from Baseline tables for blood pressure values based on the markedly abnormal blood pressure values will be presented within the Initial Period for the end of treatment, minimum post-Baseline, and maximum post-Baseline. The shift categories will be markedly abnormal, not markedly abnormal, and missing.

Combined Initial and Maintenance Period

The change from Baseline summaries described above for the Initial Period will be repeated for the Combined Initial and Maintenance Period and will be presented based on the SS and on CSS. For the summaries based on the SS, the tables that are produced will include data while on either blinded or open-label treatment.

Shift from Baseline tables for blood pressure values based on the normal range will be presented within the combined Initial and Maintenance Period for the end of treatment, minimum post-Baseline and maximum post-Baseline values. The shift categories will be low, normal, high, and missing. If a subject switches blinded CZP dose from Initial to Maintenance Period, the minimum post-baseline value, the maximum post-baseline value and the final end of treatment will be determined for each respective dose received. For the summarization of "All CZP", the minimum and maximum post-baseline value will be determined considering values reported while on either CZP dose; the final end of treatment value will reflect the values reported while on the last CZP dose received during the study.

The shift table will present shifts by treatment group from Baseline (last observation before Week 0; regardless of which study treatment was administered at Week 0) to post-Baseline minimum, maximum and end of treatment while on treatment summarized. Values observed during blinded and open-label are included.

Shift from Baseline tables for blood pressure values based on the markedly abnormal blood pressure values will be presented within the combined Initial and Maintenance Period for the end of treatment, minimum post-Baseline, and maximum post-Baseline. The shift categories will be markedly abnormal, not markedly abnormal, and missing.

10.4.2 Physical examination

The Investigator will conduct a complete physical examination in all subjects at Screening, at Baseline, at Week 16, at Week 24, at Week 52 and at SFU Visit. The physical examination will cover the following: general appearance, head, ears, eyes, nose, throat, hair, skin, respiratory, cardiovascular, gastrointestinal, musculoskeletal, hepatic, neurological, and mental status. All physical examination data will be listed; clinically relevant changes during the study will be recorded as AEs.

In addition, TB signs and symptoms will be assessed. A listing of these data will be provided including abnormalities and their classification if clinically meaningful or not.

10.4.3 12-lead electrocardiogram

A 12-lead standard electrocardiogram (ECG) will be performed at Screening, Week 24 and Week 52.

Combined Initial and Maintenance Period

Descriptive statistics will be tabulated for the following ECG variables (absolute values and change from baseline) by visit: Heart rate (HR), PQ/PR-interval, QRS-duration, QT-interval,

QTcB-interval. The results will be tabulated based on subjects in the SS and CSS considering data collected while on either blinded or open-label treatment.

Additionally, a shift table will be provided for the number and percentage of subjects with normal, abnormal not clinically significant and abnormal clinically significant ECG results from Screening to each time point considering data collected while on either blinded or open-label treatment (for the SS) and for all subjects in the CSS.

A subject data listing of all 12-lead ECG data will be provided.

10.4.4 Chest x-ray for TB

A chest x-ray must be performed in the Screening Period unless one has been performed within 3 months prior to the Screening Visit. The chest x-ray must be clear of signs of TB infection (previous or current) before first study drug administration. Further chest x-rays will be performed at Week 12, Week 24 and Week 52. Any new clinically significant findings must be documented and classified as normal, abnormal and not clinically significant or abnormal and clinically significant. Clinically relevant changes during the study will be recorded as AEs.

A shift table will be provided for the number and percentage of subjects with normal, abnormal and not clinically significant and abnormal and clinically significant results from Screening to each time point during Initial and Maintenance Period, considering data collected while on either blinded or open-label treatment (for the SS) and for all subjects in the CSS.

A subject data listing of chest x-ray results will be provided.

10.4.5 Interferon-gamma release assay (IGRA) testing for TB

All subjects will have IGRA testing conducted at Screening, Week 24 and Week 52. Results from this tuberculosis test will be reported as positive, negative, or indeterminate. A listing will be provided for both the SS and CSS.

10.4.6 Subject questionnaire for TB

The questionnaire "Evaluation of signs and symptoms of tuberculosis" will be used as a source document and will assist with the identification of subjects who may require therapy for TB. The results will not be included in the database. Therefore no analysis of the questionnaire results will be performed.

10.4.7 Pregnancy testing

Pregnancy testing will consist of serum testing at Screening and urine testing at all other applicable visits. The results of the pregnancy test will be listed.

